23.2.1. Progression criteria for stop/go

RED: end trial; AMBER: explore methods for increasing recruitment/improving LTAD safety and with permission of funder proceed with protocol revisions; GREEN: continue to main phase of trial.

	RED	AMBER	GREEN *
Pilot recruitment/total study recruitment target by end of study month 21	<10%	10-20%	≥21%
Mean recruitment rate/site/month (based on data to end of study month 21)	<0.2	0.2-0.3	>0.3
Number of sites opened by end of study month 18	<19	20-23	≥24
Total number of patients recruited by study month 21	<55	55-65	≥66
Proportion of those recruited by study month 18 retained to end of follow up*	<50%	50%-60%	>60%
Percentage of LTADs removed due to peritonitis by end of study month 21*	>15%	10%-15%	<10%
Proportion completing SFLDQoL questionnaire (except questions on sexual function) in those retained at time point, by end of month 18*			
Baseline	<90%	91%-95%	>95%
Week 4	<85%	85%-90%	>90%
Week 8	<80%	80%-85%	>85%
Week 12	<75%	75%-80%	>80%
Checklist for LTAD insertion and post procedure monitoring % completed	<75%	75%-85%	>85%

Table 6. Progression Criteria for Pilot Stop/Go

* Based on feasibility study data (46), and systematic review (44)

Assuming a successful pilot, we will then open an additional 11 sites over the next 5 months, recruiting the remaining 226 patients from a total of 35 sites over 26 months of the main trial (on average about six patients/site). This is consistent with our feasibility study recruitment (36 patients recruited across five sites over 30 months). The first eight sites, which will be open the longest, will recruit 11 patients on average; the final seven, 6 on average, over a total recruitment period of 44 months.

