23. STATISTICS AND DATA ANALYSIS

23.1. Sample size calculation

Following on from the HTA Committee and PPI feedback and the International LIverHope Consortium's recommendations (73), we have selected HRQoL as our primary outcome.

The minimal clinically important difference (MCID) is the mean change in HRQoL scores for patients reporting a minimal yet perceptible change in health between the baseline and follow-up assessments. (85) In the ongoing LiverPal Study (one of the largest palliative trial in the United States (86), an MCID of 9 points on the FACT-Hep questionnaire was used; and in a study assessing LTADs in cirrhosis (87), an MCID of 10 points was chosen (SF-36 questionnaire). While these studies show the use of the MCID to inform sample size in palliative trials, neither of the tools selected are validated in advanced cirrhosis. As we will be using the SFLDQoL, a sensitive and validated questionnaire in advanced cirrhosis (34), we have selected a MCID of 8 points.

In our feasibility REDUCe study (46), the pooled baseline mean across SFLDQoL domains (excluding sex function) was 56.4 (SD=26.1). With 93 participants in each group for the analysis, we will have 90% power for 5% significance to detect an adjusted difference in mean SFLDQoL scores of 8 points between the LTAD and LVP groups at the end of 3-months (effect size 0.31). This effect size falls within Cohen's recommended cut offs for small (0.20) to moderate (0.50) effect size. (88) We will assume a correlation between baseline and the 3 follow-up measurements of 0.48 which is the lower bound of the 95% Confidence Interval for the correlation (point estimate 0.77) (from REDUCe study data). (46) With an expected 40% attrition (REDUCe study) (46), we will recruit 310 participants in total for the trial.

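### Table 6 judges recruitment by study month 21 in two rows whose RED lines differ (fewer than 31 against fewer than 55), so 31 to 54 recruits is both AMBER and RED

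*Protocol*

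**What the plan says.** Section 23.2.1 of the protocol gives each colour an action. RED ends the trial. AMBER means looking for improvements and going on with a revised protocol if the funder permits. GREEN means continuing to the main phase.

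Two rows of Table 6 concern cumulative recruitment at the same date:

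- First row, "Pilot recruitment/total study recruitment target by end of study month 21": RED <10%, AMBER 10-20%, GREEN ≥21%.
- Fourth row, "Total number of patients recruited by study month 21": RED <55, AMBER 55-65, GREEN ≥66.

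The denominator of the first row is fixed in section 23.1: "we will recruit 310 participants in total for the trial". Section 23.3 says that the pilot data are analysed descriptively and that the DSMC makes a recommendation to the TSC. Neither section says how the rows combine or which prevails if they disagree.

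**The concern.** The fourth row is the numerator of the first, so one count should receive one colour from both. If the cut-offs disagree, the table gives opposite instructions for the same result, and the committees must choose between them after seeing recruitment. Progression criteria are fixed in advance to avoid exactly that choice. What is at stake is whether the trial ends or goes on with revisions. The treatment comparison and its error rates are not affected.

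**Working it through.** **Inputs.** Total target 310 (section 23.1); the cut-offs of the first and fourth rows (Table 6); 48 recruits planned in 12 months, 24 sites opened at two a month, one patient per site every 4 months, and 36 further recruits in the rest of the pilot period (section 23.2).

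**The target of 310.** Section 23.1 states: "With 93 participants in each group for the analysis, we will have 90% power for 5% significance". With 40% attrition, 93 / 0.60 = 155 per group, or 310 in total, as stated. The 93 can also be checked. With an 8-point difference, SD 26.1, correlation 0.48 and three follow-up measurements, the ANCOVA variance factor is (1 + 2 × 0.48)/3 − 0.48² = 0.423. Then n = 2 × (1.960 + 1.282)² × 26.1² × 0.423 / 8² ≈ 95 per group, close to 93. Also 310 − (48 + 36) = 226, the number section 23.2.1 leaves for the main phase. The denominator is sound.

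**GREEN lines.** 21% of 310 = 65.1, so at least 66 patients. The fourth row also says 66. They agree.

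**RED lines.** 10% of 310 = 31, so the first row is RED below 31. The fourth row is RED below 55, and 55/310 = 17.7%. They disagree.

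**Colour for each count:**

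| Recruits by month 21 | Share of 310 | First row | Fourth row |
|---|---|---|---|
| 0-30 | up to 9.7% | RED | RED |
| 31-54 | 10.0-17.4% | AMBER | RED |
| 55-62 | 17.7-20.0% | AMBER | AMBER |
| 63-65 | 20.3-21.0% | no colour (between 20% and 21%) | AMBER |
| 66 or more | 21.3% or more | GREEN | GREEN |

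The contradictory zone holds 54 − 31 + 1 = 24 possible counts. Rounding the percentages to whole numbers does not remove it: the zone then starts at 30, and 64-65 become GREEN in the first row and AMBER in the fourth.

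**Could another reading reconcile the rows?**

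- *Another denominator.* For 55 patients to be the 10% line, the target would have to be 541-550. For 66 to be the 21% line, it would have to be 310-314. No single target gives both.
- *Only the 48-patient cohort in the numerator.* 48/310 = 15.5%, so GREEN could not be reached even with full pilot recruitment.

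**How likely is the zone?** This step assumes that recruitment starts after study month 6, which is inferred from 24 sites open by month 18 at two a month. Month 21 is then 15 months into recruitment. Counts are taken as Poisson.

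- Planned counts: 48 in 12 months plus 3 months × 24 sites × 0.25 = 18, giving 66. P(31 to 54) = 7.5%.
- Stated rate with staggered opening: the first 12 months supply 156, 144 or 132 site-months if sites open at the start, middle or end of each month. Adding 3 × 24 = 72 gives 228, 216 or 204. At 0.25 per site-month the means are 57, 54 and 51, and P(31 to 54) = 38%, 54% and 69%.

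The two expectations differ because 0.25 per site-month over 132-156 site-months yields only 33-39 patients in the first 12 months, not 48.

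**The case against.** The best defence is that the table is not applied mechanically. The data are described, the DSMC advises and the TSC weighs all criteria together. The cut-offs concern accrual, so choosing between them late does not bias the treatment estimate or inflate type I error. Both statements are true and limit the consequences. They do not remove the contradiction, because the protocol attaches a definite action to each colour.

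A rule that the worst row governs would settle 31-54 as RED. The protocol states no such rule, and under it the first row's RED line could never decide anything.

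Three stronger readings are tempting, and the documents do not support them:

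- *That the rate row is a third conflicting RED line.* "Mean recruitment rate/site/month (based on data to end of study month 21") is a rate per site, not a count. A low count with an acceptable rate can point to late site opening, so a different colour there is information. It converts to a patient number only if sites open exactly as planned.
- *That the plan itself makes the conflict likely.* This holds for the stated rate with staggered opening, but the planned counts lead to 66 by month 21 and a chance of about 7.5%. Section 23.2 supports both expectations.
- *That 55 is the right stopping line.* Nothing shows whether 10% or 55 was intended.

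**Conclusion.** Table 6 is wrong as written. For one quantity at one date it sets RED at fewer than 31 and at fewer than 55, so 31 to 54 recruits means both going on with revisions and ending the trial. Counts of 63-65 have no colour in the first row. Both results rest only on the printed cut-offs and the target of 310.

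The chance of landing in 31-54 is less certain: about 7.5% with a mean of 66, and about 38-69% with means from 57 down to 51. These figures depend on the inferred month-6 start, on Poisson counts, and on which of the two accrual expectations in section 23.2 is used. The sample size and the primary analysis are untouched.

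**What to change.** Before the pilot review, the sponsor should reconcile the two rows to one set of cut-offs, with the agreement of the TSC and funder. Either direction removes the conflict:

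- *If 55 was the intended stopping line:* delete the first row, or restate it as the equivalent of the fourth: RED <17.7%, AMBER 17.7% to <21.3%, GREEN ≥21.3%. These are 55/310 and 66/310 rounded to one decimal. Because 66/310 is 21.29% unrounded, the row should give the fractions or the rounding rule.
- *If 10% was the intended stopping line:* change the fourth row to RED <31, AMBER 31-65, GREEN ≥66, and close the first row's gap between 20% and 21%.

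The rate row is a separate criterion and need not be derived from the counts. The cost is one table edit by protocol amendment, with no effect on patients or data collection.

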23.2. Internal pilot

An 18-month internal pilot will assess recruitment and LTAD safety: 12 months recruitment, three months' follow up, one-month for analysis, two-months' for a STOP/GO decision. We will recruit 48 patients to allow estimation of recruitment rate & retention with a margin of error of 15% assuming 60% retention. With an expected rate of one patient recruited per site every 4 months, this could be achieved with 24 sites (2 sites opened each month) over 12-months' recruitment. During the final follow up, analysis & STOP/GO decision period of the internal pilot, recruitment (n=36) would continue in the pilot sites in preparation for the main trial.

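### The planned rate of 0.25 patients per site per month, the pilot headcounts of 48 and 66, and the GREEN limit of more than 0.3 in Table 6 do not fit together

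*Protocol*

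**What the plan says.** Section 23.2 gives the only stated planning rate: "With an expected rate of one patient recruited per site every 4 months", which is 0.25 per site per month. It then says of the first 48 patients that "this could be achieved with 24 sites (2 sites opened each month) over 12-months' recruitment". The number itself is justified by precision: "We will recruit 48 patients to allow estimation of recruitment rate & retention with a margin of error of 15% assuming 60% retention". For the remaining six months of the pilot, "recruitment (n=36) would continue in the pilot sites in preparation for the main trial".

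Table 6 in section 23.2.1 has four rows that bear on this:

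| Row | RED | AMBER | GREEN |
|---|---|---|---|
| "Mean recruitment rate/site/month (based on data to end of study month 21") | <0.2 | 0.2-0.3 | >0.3 |
| "Total number of patients recruited by study month 21" | <55 | 55-65 | ≥66 |
| Pilot recruitment as a share of the total target, by month 21 | <10% | 10-20% | ≥21% |
| "Number of sites opened by end of study month 18" | <19 | 20-23 | ≥24 |

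RED means ending the trial. AMBER means looking for ways to improve recruitment and continuing with protocol revisions if the funder permits. The text after the table plans a further 226 patients from 35 sites over 26 months, with 11 sites added over 5 months and 44 months of recruitment in all. It calls this consistent with the feasibility study: "36 patients recruited across five sites over 30 months".

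**The concern.** The expected rate of 0.25 is the midpoint of the AMBER band on the rate row, yet GREEN on the count row (66) equals the plan's own headcount at month 21. One plan is therefore judged by two yardsticks that imply different recruitment rates. The 48-patient pilot figure also appears to assume sites are open longer than the opening schedule allows.

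The stake is the stop/go decision. If sites perform at the stated rate, the table will probably report AMBER on rate and may well report RED on headcount, simply because the limits were not derived from that rate. The committees would then be reading an inconsistency in the plan as a recruitment failure.

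**Working it through.** **Inputs.** Rate 0.25; two sites per month to 24; 48 then 36 patients; 226 patients, 35 sites, 26 months; Table 6 limits (all sections 23.2 and 23.2.1). Two assumptions are needed. First, study month 18 is recruitment month 12, because the GREEN limit of 24 sites open by month 18 matches the end of the opening schedule. Study month 21 is then recruitment month 15. Second, a site counts only once it is open. Results are given for sites counted from the start / middle / end of their opening month.

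**Figures that reproduce at or near 0.25**
- Last six pilot months: 24 × 6 × 0.25 = 36, as stated.
- Feasibility: 36/(5 × 30) = 0.24, if all five sites were open throughout.
- Main phase: 24 × 26 site-months plus 11 sites opening evenly over 5 months gives 888 / 882.5 / 877, so 226 patients needs 0.254 / 0.256 / 0.258.

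**Figures that do not**
- Open site-months to recruitment month 12: 156 / 144 / 132. At 0.25 this gives 39 / 36 / 33 patients, not 48. Reaching 48 needs 0.308 / 0.333 / 0.364. Put another way, 48/(24 × 0.25) = 8 months open per site on average, against 6.5 / 6.0 / 5.5 under the schedule.
- Open site-months to month 21: add 24 × 3 = 72, giving 228 / 216 / 204. At 0.25 this gives 57 / 54 / 51 patients. The plan's headcount is 48 + 18 = 66 (the 18 being half of the 36), which implies 0.289 / 0.306 / 0.324.

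**What the rows would report at a true 0.25** (Poisson count with mean 57 / 54 / 51)

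| | Start | Middle | End |
|---|---|---|---|
| Patients needed for rate >0.3 | 69 | 65 | 62 |
| P(GREEN), rate row | 6.7% | 8.0% | 7.4% |
| P(RED), rate row | 6.0% | 7.3% | 6.7% |
| P(GREEN), count row (≥66) | 13.1% | 6.2% | 2.5% |
| P(RED), count row (<55) | 37.8% | 53.6% | 69.4% |

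If site rates vary (gamma distribution, an assumption), P(GREEN) on the rate row rises to 12-13% at a coefficient of variation of 0.5 and 20-21% at 1.0. At the feasibility rate of 0.24 without such variation it is 3.5-4.3%.

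The expected 51-57 patients are 16-18% of 310, which is AMBER on the percentage row, while the lower part of that range is RED on the count row.

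**Rate the trial needs.** Pilot site-months over 18 months are 300 / 288 / 276. Adding the main phase gives 1188 / 1170.5 / 1153 over 44 months. Then 310/1188 = 0.261 and 310/1153 = 0.269. At 0.25 the yield is 297 / 293 / 288, a shortfall of 13-22. With 35 sites at 0.25 (8.75 patients a month), that is 1.5-2.5 more months. A sustained 0.3 would yield about 346-356.

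**The case against.** A reader might infer that a trial recruiting exactly as planned would nearly always miss GREEN on the rate row. The document does not support that. The plan is also its headcounts, and 66 patients by month 21 is 0.289-0.324 per open site-month, on either side of 0.3. With a Poisson mean of 66, P(GREEN) on the rate row is 37-71%. Measured against the headcounts, the limit is roughly coherent and 0.25 is the figure that does not fit.

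Nor can it be said that AMBER would flag a trial that is on course: 0.25 falls 13-22 patients short of 310 in 44 months, so a prompt to look at recruitment is defensible. A GREEN limit somewhat above the expected rate may also be deliberate. AMBER does not stop the trial, and section 23.3 routes the decision through the DSMC and TSC on descriptive data.

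These points stand. They limit the claim about the 0.3 limit but leave the inconsistency, because no single rate gives 0.25, 48 and 66 under the stated opening schedule. They also show that the count row matters more: at 0.25 it is far likelier than the rate row to read RED. Lowering the rate limit alone would not help. GREEN at 0.26 corresponds to 53-59 patients by month 21, which is AMBER or RED on count.

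**Conclusion.** The stated rate, the pilot headcounts and the GREEN limit on rate are mutually inconsistent. At 0.25 the schedule gives 33-39 patients at recruitment month 12 against 48 planned, and 51-57 at month 21 against 66. Such a trial would reach GREEN on rate about 7-8% of the time (12-21% with assumed site variation) and would be RED on headcount about 38-69% of the time. The limit of 0.3 is also above the 0.26-0.27 that delivers 310 in 44 months.

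The probabilities rest on the month mapping, on counting open site-months, on sites opening on schedule and, for the headline figures, on Poisson variation. The protocol does not define the denominator, and the choice matters: 24 sites × 15 months gives 66/360 = 0.18, which is RED on rate for a pilot that is GREEN on count. The feasibility rate would be higher if its sites opened late. The finding is worth correcting but does not threaten the trial's validity, since it concerns the progression rule and not the treatment comparison.

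**What to change.** 1. In Table 6, define the rate's denominator as open site-months, and state when a site starts to count.
2. Choose one planning rate that delivers 310: about 0.26-0.27 per open site-month in 44 months, or 0.25 with about 2 more months of recruitment.
3. From that rate and the opening schedule, derive the rate row, the count row, the percentage row and the 48-patient figure in section 23.2. At the required rate the schedule gives about 35-41 patients at recruitment month 12 (0.269 × 132 to 0.261 × 156) and 55-59 at month 21 (0.269 × 204 to 0.261 × 228).
4. Set the RED limits on the rate, count and percentage rows at matching values, so that one headcount cannot be AMBER on one row and RED on another.

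The cost is that several Table 6 limits and the pilot headcount must be restated and agreed with the TSC and funder, and the early headcounts become lower. The precision argument for 48 also needs restating: the retention margin at n = 48 is 1.96 × √(0.6 × 0.4/48) = 13.9%, and 15% needs about 41 patients, so little precision is lost at the upper end of 35-41.

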Routine ascitic fluid analysis in the LVP group will be performed at each drainage as is currently standard of care. In the LTAD group, routine ascitic fluid analysis will not be performed due to the likelihood of growing skin contaminants (80), the clinical significance of which remains uncertain. In those with a LTAD, ascitic fluid analysis will **ONLY** be performed if there is clinical suspicion for peritonitis: fever, abdominal pain, increased white cell count, worsening hepatic decompensation or renal function. In such instances the ascitic fluid sample will be taken for analysis from both the LTAD as well as via a separate ascitic tap. Peritionitis will be diagnosed if ascitic fluid neutrophil count is > 250/mm³, and or ascitic fluid white cell count is >500/mm³ and or if ascitic fluid culture is positive. (9, 64) Peritonitis will be treated as per current guidelines. (9, 64) Development of peritonitis will not necessarily mandate LTAD removal. This needs to be decided on a **case-by-case basis** after discussion between site teams and the CI.

LTAD (Group 1) post drain insertion care (also see Figure 1)

- The research team will explain to the patient and informal caregivers how the LTAD will be used and provide them with the drainage kit, which will include at least two weeks supply of drainage bags. The Research teams will provide patients with the LTAD manufacturer information sheet and discharge letter, the latter also being sent to the GP and community nursing team. The discharge letter will state that patients have been discharged with a LTAD. LTAD manufacturer details are included in the discharge letter. An additional community nurse referral will be sent to the community teams with basic instructions on LTAD management.
- The research team will also contact the appropriate lead community nurse to update them. This will ensure that home visits can be organised by the community team to

perform recurrent drainage and arrange necessary disposal of clinical waste. The research team will also inform the LTAD manufacturer so that they can organise additional bespoke training and support for participants/informal caregivers if needed and ensure supply of drainage bags

• The patient and community teams will be provided with the contact number for the research team. The patients will also be provided with written information describing LTAD management should they be admitted to hospital out of hours so that clinical teams are aware.

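### Table 6 gives both AMBER and RED for 31 to 54 patients at month 21, and its rate row places the planned 0.25 patients per site per month in AMBER

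*Protocol*

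**What the plan says.** Protocol 23.2 sets the pilot accrual assumptions: "With an expected rate of one patient recruited per site every 4 months", and "this could be achieved with 24 sites (2 sites opened each month) over 12-months' recruitment". The pilot target is 48 patients, with 36 more recruited while follow-up, analysis and the decision are completed. The overall target is 310 (23.1).

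Table 6 in 23.2.1 then gives the traffic-light bands. RED means ending the trial, AMBER means revising with the funder's permission, and GREEN means continuing. The four recruitment rows are:

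| Row | RED | AMBER | GREEN |
|---|---|---|---|
| 1. "Pilot recruitment/total study recruitment target by end of study month 21" | <10% | 10-20% | ≥21% |
| 2. Mean rate per site per month, to month 21 | <0.2 | 0.2-0.3 | >0.3 |
| 3. Sites open by month 18 | <19 | 20-23 | ≥24 |
| 4. "Total number of patients recruited by study month 21" | <55 | 55-65 | ≥66 |

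Section 23.3 has the Data and Safety Monitoring Committee (DSMC) make a recommendation to the TSC. Neither section says how rows that show different colours are combined.

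**The concern.** Rows 1 and 4 look like one criterion written twice, once as a share of 310 and once as a head count. If so, their cut-offs should coincide. They do at GREEN but not at RED. A pilot landing between the two RED cut-offs could be reported either as one to revise or as one to close, and either report would be faithful to the table.

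The rate row raises a second question: whether a pilot recruiting at its own planned rate can be GREEN on that row.

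At stake is the main purpose of pre-specified progression criteria, which is to fix the decision before the data are seen.

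**Working it through.** **Inputs.** Target 310 (23.1). Rate 1/4 = 0.25 per site per month; 24 sites opening two per month; 48 patients in 12 months, then 36 more (23.2). Bands from Table 6. One inference: 24 sites are due by study month 18, so study month 18 is taken as recruitment month 12 and study month 21 as recruitment month 15.

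**Step 1: the plan's own figures.** Credit each site with one patient for every 4-month block it has started. Sites open k months then contribute ceil(k/4), with two sites for each k.

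- Recruitment month 12: 8×3 + 8×2 + 8×1 = 48, as stated.
- Recruitment month 15: 6×4 + 8×3 + 8×2 + 2×1 = 66, the GREEN count in row 4.
- Recruitment month 18: 4×5 + 8×4 + 8×3 + 4×2 = 84 = 48 + 36, leaving 310 − 84 = 226, as stated.
- Month 44: 8×11 + 8×10 + 8×9 + 4×7 + 7×6 = 310. The 11 and the 6 per site are stated; the 7 for the four sites in between is inferred.

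So the accrual figures hang together under one convention.

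**Step 2: rows 1 and 4 on one scale.**

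- Row 1 in patients: 10% × 310 = 31; 20% × 310 = 62; 21% × 310 = 65.1, so 66.
- Row 4 as percentages: 55/310 = 17.7%; 66/310 = 21.3%.
- The rows measure the same thing. The GREEN cut-offs match at 66, and row 1 cannot be about the 48-patient pilot cohort alone, because 48/310 = 15.5% could never reach 21%.

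| Patients at month 21 | Share of 310 | Row 1 | Row 4 |
|---|---|---|---|
| ≤30 | ≤9.7% | RED | RED |
| 31-54 | 10.0-17.4% | AMBER | RED |
| 55-62 | 17.7-20.0% | AMBER | AMBER |
| 63-65 | 20.3-21.0% | no band | AMBER |
| ≥66 | ≥21.3% | GREEN | GREEN |

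The conflict spans 54 − 31 + 1 = 24 possible counts.

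**Step 3: the rate row.** The planned 0.25 lies inside AMBER (0.2-0.3). The feasibility study that 23.2.1 cites as consistent with the plan recruited 36 patients at five sites over 30 months: 36/(5×30) = 0.24, also AMBER.

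**Step 4: how far the result depends on counting.** Site-months actually open at recruitment month 12, if sites open at the start, middle or end of each month, are 156, 144 or 132. Three more months at 24 sites add 72, giving 228, 216 or 204 at month 15.

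- Strict accrual at 0.25: 39, 36 or 33 patients at month 12 and 57, 54 or 51 at month 15 (18.4%, 17.4% or 16.5% of 310).
- The plan's convention credits 48×4 = 192 site-months at month 12, against 132-156 open.
- With 66 patients, rows 1 and 4 are GREEN. Row 2 then reads 66/228 = 0.289 (AMBER), 66/216 = 0.306 (GREEN) or 66/204 = 0.324 (GREEN).

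**Step 5: remaining gaps.** Row 3 is RED below 19 and AMBER from 20, so 19 sites has no colour.

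**The case against.** The strongest reply is that Table 6 guides judgement and does not act automatically. The DSMC recommends, the TSC decides what to pass on, and AMBER lets the trial continue with revisions. That is fair, and it means no count ends the trial by itself. It does not settle what colour 31-54 patients is, because RED is given a plain meaning and the table assigns it on one row only. A worst-colour rule would resolve the clash, but none is written, and it would leave row 1's 10% cut-off with no function.

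Several stronger readings are tempting and are not supported.

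- *That 48 and 66 do not follow from the stated rate and openings, or that 44 months would yield 288-297 patients instead of 310.* Step 1 reproduces 48, 66, 84, 226 and 310. The convention is optimistic and unstated, but it is consistent.
- *That a pilot on plan must miss GREEN on every recruitment row.* On the plan's own schedule 66 patients is GREEN on rows 1 and 4. Only strict site-month accrual misses all three patient-recruitment rows.
- *That retention GREEN should be ≥60% instead of >60%.* With 48 patients, 60% is 28.8, so both wordings need 29.
- *That baseline questionnaire completion between 90% and 91% is a live gap.* With 48 patients the attainable values are 43/48 = 89.6% and 44/48 = 91.7%.
- *That the row "Percentage of LTADs removed due to peritonitis by end of study month 21" is defective because "Development of peritonitis will not necessarily mandate LTAD removal".* The row does track a case-by-case decision, but it continues the feasibility study's removal criterion. Peritonitis is also a secondary outcome, and adverse events go to the DSMC. Adding an infection band is a design preference.

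**Conclusion.** The point stands as an inconsistency in the decision thresholds. Rows 1 and 4 of Table 6 give different colours for 31-54 patients (10.0-17.4% of the target), one of them RED, with no rule for which prevails. This follows directly from the table and the target of 310 and needs no accrual assumption. The nominal planned rate of 0.25 is AMBER on row 2, so that row asks for more than the plan. Exactly 19 sites has no band, and 63-65 patients has none on row 1.

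The conflict zone is not remote. Under strict accrual with sites opening mid-month or at month end, the planned rate gives 54 or 51 patients, inside it. With openings at the start of the month it gives 57, just outside. Under the plan's own convention it gives 66, well clear. These comparisons rest on reading study month 21 as recruitment month 15.

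The thresholds should be corrected before the stop/go decision. Nothing here shows the sample size or the accrual totals to be miscalculated.

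**What to change.** 1. Delete row 1, or derive rows 1 and 4 from one set of counts. If a percentage is kept, choose one that reproduces the counts. A rounded 18% does not quite do so: 18% × 310 = 55.8, which would make 55 patients RED on row 1 and AMBER on row 4. A cut of 17.5% works (17.5% × 310 = 54.25): RED <17.5%, AMBER 17.5% to <21%, GREEN ≥21%. This also closes the 20-21% gap.
2. Align the rate row with the planned 0.25, or state that GREEN is deliberately set above plan and why. Say in 23.2 how site-months are counted, and use the same rule for the count rows. Otherwise 0.25 per open site-month (51-57 patients) and the GREEN count of 66 will still disagree.
3. Assign 19 sites to a band.
4. State how rows with different colours combine.

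The cost is a short edit to Table 6 and 23.2, agreed with the TSC and funder. No new data are needed, and the figures 48, 66, 84, 226 and 310 can stay once the counting rule is written down.
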